## 2. Specific Aims and Objectives

**Aim 1: Refine RT-CA.** We will conduct a single-arm open pilot of RT-CA (N=5 dyads) to evaluate initial feasibility and acceptability using exit interviews and pre-post assessments.

Findings from Aim 1 will then inform the next iteration of the RT-CA manual and feasibility trial.

**Aim 2: Conduct medical record review** of all admitted cardiac arrest patients at MGH during the study period (N = 200-400). We will collect basic cardiac arrest clinical data on these patients to determine the representativeness of our sample in Aim 1 to all cardiac arrest admissions at MGH and the United States.

Findings from Aim will inform recruitment gaps, if any, and contextualize the recruitment pool at MGH relative to the United States.

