## 3. General Description of Study Design

We are proposing an open pilot trial of RT-CA with 5 CA survivor-caregiver dyads. All dyads will undergo the 6-session intervention. The first session will be at the bedside (unless the survivor is discharged before session 1 takes place, at which point we will meet over Zoom or telephone (Doximity)). The remaining sessions will be conducted over Zoom or telephone (Doximity) depending on participant preference.

Parallel to our open pilot, we propose to conduct medical record of all admitted cardiac arrest patients at MGH during the study period and maintain them in a study log (N = 100-300). As part of our recruitment efforts (see sections 4 and 5), we will pre-screen Epic ICU and stepdown floor rosters in order to identify all cardiac arrest patient admissions, who could be eligible for our open pilot. By including all admissions into a study log we will be able to 1) monitor cardiac arrest patients' mental status during their hospital stay to see if they will become eligible for our open pilot and 2) determine the representativeness of the open pilot sample's cardiac arrest clinical characteristics.

We will need to access the medical records of all cardiac arrest admissions to monitor them throughout their stay in the hospital. If the patient recovers good neurological status, they may be eligible for our study, at which point we will follow our recruitment and enrollment procedures as detailed below. There is no guarantee that a patient with cardiac arrest recovers neurological status, so we will need to conduct daily pre-screening of their neurological exam until they become potentially eligible or are discharged.

Additionally, we will need to collect basic cardiac arrest clinical data of all cardiac arrest admissions in order to contextualize our study sample in the context of cardiac arrest admissions at MGH and the US overall. This information is routinely collected and reported in cardiac arrest research. We will need to be able to identify if our enrolled sample is representative of the greater population, and if not, we will need to report the disparities that exist in our enrolled sample.

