#### **4. Subject Selection**

We will recruit and enroll dyads from MGH ICUs and stepdown floors. The majority of cardiac arrest (CA) survivors are initially cared for in the Heart Center Intensive Care Units and stepdown floors, while a minority are also cared for in the Neuro-ICU, Medical Intensive Care Unit, and Cardiac Surgical Intensive Care Unit, and corresponding stepdown floors.

During phase 1 of this study, the PI presented to staff from these ICUs and stepdown floors that care for CA survivors on the overall study aims, purpose, potential benefits to participants, and best ways to facilitate referrals.

Trained study staff will identify new CA survivors primarily through daily pre-screening of ICU and stepdown survivor rosters. We will also obtain referrals from the medical, nursing, or social work team members that are clinically caring for survivors and caregivers on service, whom the PI presented to during phase 1 of the overall study. A new CA survivor is defined as any survivor with a new diagnosis of "cardiac arrest" and documented loss of pulse in their medical record. Study staff will always confirm with a clinical team member about whether screened survivors might be appropriate study candidates before approaching to discuss our study.

Through pre-screening of ICU and stepdown floor patient rosters on Epic, our research assistant (RA) will identify CA survivors and add them to a "cardiac arrest admissions log" stored on REDCap of all CA survivors admitted to MGH during the study period. The cardiac arrest admissions log will serve to aid the RA in monitoring all currently admitted CA survivors' neurological exams to see if they will become eligible for the study. Specifically, the RA will conduct daily review of all currently admitted CA survivors' neurological exam daily as documented in the electronic medical record. The RA will specifically attend to the survivor's documented alertness, orientation, and speech output. The majority of cardiac arrest

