admissions will not regain sufficient neurological function to participate in our open pilot, however, we will keep their basic clinical cardiac arrest characteristics in the admissions log for the duration of the study so that we can then compare our open pilot sample's characteristics to the characteristics of cardiac arrest admissions at MGH, and compare the cardiac arrest admissions at MGH to cardiac arrest patients in the United States. This information is routinely collected and reported in cardiac arrest research. We will need to be able to identify if our enrolled sample is representative of the greater population, and if not, we will need to report the disparities that exist in our enrolled sample.

Should the neurological exam demonstrate focal neurologic recovery (i.e., awake, alert and oriented), the RA will send a Voalte message to survivor's bedside nurse [or other clinician known to the survivor] to confirm recovery of focal neurological status and to ask the survivor for permission to be contacted by our team to explain the study (either in person or over phone if the survivor is discharged before we are able to approach).

Medical and/or social work partners caring for CA survivors that may benefit from our study have volunteered to provide basic information of our study (the same information listed on our study flyer, which they will give to such survivors) and ask the patients for their permission to refer them to us through the Voalte messaging system.

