**All measures will be administered at both timepoints unless otherwise stated:**

- Demographics (baseline only)
- Charlson Comorbidity Index (baseline only)
- Barthel Index (survivor only)
- Modified Rankin Scale (survivor only)
- Mini Mental State Exam (survivor only; baseline only)
- Cerebral Performance Category Scale (survivor only)
- Telephone Interview for Cognitive Status (survivor only)
- Clinical Covariates Pre-test (survivor only)
- Clinical Covariates Post-test (survivor only)
- Hospital Depression and Anxiety Scale (HADS)
- Post-Traumatic Stress Disorder Checklist – 5
- The Cognitive and Affective Mindfulness Scale-Revised (CAMS-R)
- ENRICH Social Support Inventory
- Measure of Current Status Part A (MOCS-A)
- Mental Health Resource Usage
- Credibility and Expectancy Questionnaire (CEQ) (original measure administered at pre-test; measure was also adapted to be administered post-test to examine credibility and expectancy after having completed the program).
- Client Satisfaction Questionnaire (CSQ-3; post-test only)
- WHO Quality of Life-Brief
- Dyadic Relationship Scale
- Dyadic Coping Inventory
- Applied Mindfulness Scale
- Preparedness for Caregiving Scale (cargiver only)
- Meaning in Life Questionnaire
- 4 cardiac items from the Anxiety Sensitivity Index
- Gratitude Questionnaire Six Item Form

To understand the CA clinical characteristics of all admitted CA patients at MGH, we also request a waiver of consent to collect the following from the electronic medical record of all logged patients. These characteristics will also be logged for the open pilot patients:

- Cardiac arrest location
- Time until return of spontaneous circulation (ROSC)
- Initial cardiac arrest rhythm
- Age, sex

Each member of the dyad will receive up to \$60 in compensation (\$20 for baseline assessments and \$40 for post-test assessments). Payment will be made as gift cards.

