## 9. Statistical Analysis

For open pilot quantitative data, we will assess the feasibility benchmarks (recruitment, assessments, adherence, therapist fidelity) and acceptability benchmarks (satisfaction, credibility) (see **Table 1**) through frequencies and proportions. For qualitative data, we will examine exit interviews using thematic analysis. We will then conduct mixed methods analysis using an explanatory-sequential design, which allow us to integrate quantitative and qualitative data to refine the RT-CA manual and study procedures. We will use the exit interviews to explain the open pilot quantitative findings.

**Table 41** Feasibility and Acceptability Benchmarks.

Outcome	Benchmark
Feasibility (>70% Acceptable; >80% Excellent)	
Recruitment	% Eligible dyads who participate
Assessments	% Dyads with no measures missing
Adherence	% RT-CA dyads that complete 4/6 sessions
Therapist Fidelity	% RT-CA selected sessions (20%) (100% adherence on Fidelity Checklist)
Acceptability (>70% Acceptable; >80% Excellent)	
Treatment Acceptability	% RT-CA dyads score above midpoint on Client Satisfaction Questionnaire-3
Credibility and Expectancy	% RT-CA dyads score above midpoint on Credibility/Expectancy Questionnaire
Adverse Events	(Minimal/None)

For contextualizing the clinical cardiac arrest characteristics of our open pilot sample, we will conduct chi square and Wilcoxon rank sum tests for categorical and continuous variables to examine differences in our open pilot sample compared to all MGH cardiac arrest admissions, and all cardiac arrest admissions in the US as reported by the AHA.

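### Section 9's tests of the 5-survivor pilot against MGH and the US do not fit the data: the groups overlap, the US side is probably summary figures, the stated MGH-versus-US comparison has no method, and the log size is given two ways

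*Combined protocol and SAP*

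**What the plan says.** - **Size of the pilot.** Section 3: "We are proposing an open pilot trial of RT-CA with 5 CA survivor-caregiver dyads". Five survivors therefore contribute arrest characteristics.
- **Purpose.** Section 3, repeated in Section 4: "We will need to be able to identify if our enrolled sample is representative of the greater population". Both sections add that disparities will be reported if it is not.
- **Tests.** Section 9: "we will conduct chi square and Wilcoxon rank sum tests for categorical and continuous variables to examine differences in our open pilot sample". The comparators are all MGH cardiac arrest admissions "and all cardiac arrest admissions in the US as reported by the AHA". No significance level, exact method, one-sample method or US dataset is named.
- **Variables.** Section 6 lists arrest location, time to ROSC, initial rhythm, age and sex.
- **Who is in the log.** Section 4 describes a log "stored on REDCap of all CA survivors admitted to MGH during the study period". Section 6 adds: "These characteristics will also be logged for the open pilot patients".
- **MGH against the US.** Section 4 says the team will "compare the cardiac arrest admissions at MGH to cardiac arrest patients in the United States". Aim 2 in Section 2 says the findings will "contextualize the recruitment pool at MGH relative to the United States". The testing sentence in Section 9 covers only differences in the pilot sample.
- **Size of the log.** 200–400 under Aim 2 in Section 2; 100–300 in Section 3.

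**The concern.** Both named tests assume two separate groups, and rank-sum also needs a value for every individual in each group. The MGH comparison departs from the first condition. The US comparison probably departs from the second. The comparison with real information in it, the whole log against the US, is stated as a purpose but has no analysis.

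What is at stake is how Aim 2 is reported. If five survivors are tested and nothing reaches significance, a reader could take that as reassurance that the sample is representative, which so small a sample cannot give. Meanwhile the log, which could describe the MGH pool with useful precision, would have no pre-specified analysis against the US.

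**Working it through.** The plan gives no alpha, effect size or derivation of N for Aim 2, so there is no figure of its own to reproduce. Inputs from the documents: 5 pilot survivors (Sections 2 and 3); log N of 100 to 400 (outer limits of Sections 2 and 3). Assumptions: two-sided 5% level, two-category variables, and category shares of 10–50%, because the documents give no MGH or US values.

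**1. Overlap.** 5/100 = 5% and 5/400 = 1.25% of the log. Chi-square (no continuity correction) was enumerated: sum Bin(i; 5, p1) × Bin(j; N−5, p2) over all tables with p ≤ 0.05. The comparator count is j out of N−5 for separate groups, and j+i out of N when the five are counted on both sides. True size (p1 = p2):

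| Share | N=100 separate | N=100 overlapping | N=400 separate | N=400 overlapping |
|---|---|---|---|---|
| 10% | 5.7% | 3.7% | 7.0% | 6.3% |
| 20% | 4.3% | 3.1% | 5.3% | 5.2% |
| 30% | 3.3% | 2.7% | 3.1% | 3.1% |
| 40% | 4.2% | 2.7% | 2.6% | 2.0% |
| 50% | 5.4% | 4.6% | 6.2% | 6.2% |

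The overlap never raises the rejection rate here. It costs some power: at N=100, for 50% in the pilot against 20% elsewhere, 33% instead of 40%.

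**2. Rank-sum.** Ranks are formed from pooled individual values. Against the MGH log both sides have them, so the test can be run. Its power is about 53–57% for a 1 SD shift (simulation, normal data, N=100 to 400). Against a published mean, median or percentage there is nothing to rank.

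**3. Chi-square against a fixed US share p0.** X² = (x − 5p0)² / (5p0(1 − p0)); reject if X² ≥ 3.84; size = sum of Bin(x; 5, p0) over rejected x.

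| p0 | Rejected x | Size |
|---|---|---|
| 10% | 2–5 | 1 − 0.59049 − 0.32805 = 8.1% |
| 20% | 3–5 | 0.05120 + 0.00640 + 0.00032 = 5.8% |
| 30% | 4, 5 | 0.02835 + 0.00243 = 3.1% |
| 40% | 5 | 0.01024 = 1.0% |
| 50% | 0, 5 | 2 × 0.03125 = 6.3% |

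Expected pilot counts are 5p0 and 5(1 − p0): 0.5 and 4.5 at 10%, 2.5 and 2.5 at 50%. Chi-square and the exact binomial can disagree: 2/5 against 10% gives p = 0.025 and 0.081. At 30% and 40% they reject the same outcomes. The smallest two-sided exact p against 50% is 2 × 0.5⁵ = 0.0625, so that test can never reject there.

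**4. Power, pilot against non-enrolled log patients (N=100 and N=400).**

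| Pilot vs log | Chi-square | Fisher |
|---|---|---|
| 80% vs 50% | 28%, 33% | 9%, 13% |
| 50% vs 20% | 40%, 47% | 27%, 27% |

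**5. Precision (exact 95% intervals).** Pilot, 3/5: 14.7–94.7%. Log at a 50% share: 39.8–60.2% (N=100), 45.0–55.0% (N=400). Exact binomial power of the log to detect 60% against a US value of 50% is 46% at N=100 and 98% at N=400.

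**6. Log size.** 200–400 and 100–300 agree only over 200–300.

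**The case against.** The strongest reply is that chi-square does not behave badly here and that exact tests are partly a matter of taste. Against the log its true size is 2.6–7.0% with separate groups and 2.0–6.3% with the overlap as written, and swapping to Fisher costs power. That stands. A reader might infer that chi-square is invalid or grossly inflated at n=5; the figures support only a rough approximation that errs in both directions.

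Second, the pilot is selected by design: Section 4 requires recovered neurological status, a cognitive screening score and distress in at least one dyad member, and says most admissions will not recover enough to take part. Real differences from all admissions are plausible, so false alarms are not the main risk. This also stands, and it favours estimation over testing.

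Third, the form of the AHA data is not known. The reference list includes a 2022 AHA statistics update (reference 18), but Section 9 does not cite it. Section 11 says no data will come from outside collaborators, which does not rule out a public dataset. So one cannot say that rank-sum is impossible for the US comparison, only that it is if the figures are summaries.

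Two further inferences fail. The plan never says that non-significance will be reported as representativeness; it commits to reporting disparities. And the shift between US patients in Section 4 and US admissions in Section 9 is not a contradiction, since Aim 2 uses both terms interchangeably for MGH.

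**Conclusion.** The point holds, at low severity. Established from the text alone: the pilot survivors sit inside their own comparator; the stated MGH-versus-US comparison has no method in Section 9; and the log has two expected sizes. The overlap is small and lowers the rejection rate. The rank-sum problem is conditional on summary US data and does not touch the MGH comparison.

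The more important limit is information. Chi-square's true size is about 3–7% against non-enrolled log patients and 1–8% against a fixed reference. Power at n=5 is low with every test except for very large differences, so a non-significant result is not evidence of representativeness. These figures rest on assumed shares, two categories and a two-sided 5% level; initial rhythm may have more categories, and the rank-sum power assumes normal data although time to ROSC may be skewed. Only the descriptive Aim 2 is affected.

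**What to change.** In Section 9:

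- Make the pilot comparison a descriptive table: counts and exact 95% intervals for the pilot, beside the MGH and published US values.
- If tests against MGH are kept, compare with admissions not enrolled in the pilot. Note that exact tests hold the error rate but cost power, and that a two-sided exact binomial at n=5 cannot reject a 50% reference.
- State that a non-significant result will not be reported as representativeness.
- For age and time to ROSC against the US, report medians or means beside the published value instead of rank-sum, unless a patient-level US source is named.
- Add a one-sample comparison of the MGH log with published US proportions, with 95% intervals, for location, initial rhythm (category by category) and sex.

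In Sections 2 and 3, state one expected N range for the log.

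The cost is a few sentences and one reconciled range, with no new patient data. The team must check which variables the AHA source reports and in what form.

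### Aim 2 asks whether a 5-survivor pilot is representative, but section 9 gives only tests for difference, which cannot establish that it is

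*Combined protocol and SAP*

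**What the plan says.** Section 2 gives the purpose of the record review under Aim 2: "to determine the representativeness of our sample in Aim 1 to all cardiac arrest admissions at MGH and the United States". Section 3 turns this into a finding that has to be made: "We will need to be able to identify if our enrolled sample is representative of the greater population, and if not", the differences are to be reported. Section 4 repeats the condition: "if not, we will need to report the disparities that exist in our enrolled sample".

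The analysis is in the last paragraph of section 9: "we will conduct chi square and Wilcoxon rank sum tests for categorical and continuous variables to examine differences in our open pilot sample", against all MGH admissions and against US admissions as reported by the AHA. That paragraph presents the aim as putting the pilot in context. It states no alpha, smallest difference of interest, equivalence margin, interval or power.

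The pilot is small: "We will conduct a single-arm open pilot of RT-CA (N=5 dyads", so there are 5 survivors. The log size is given in section 2 as "all admitted cardiac arrest patients at MGH during the study period (N = 200-400" and in section 3 as "maintain them in a study log (N = 100-300". Section 6 lists the logged variables (arrest location, time to ROSC, initial rhythm, age and sex) and says that they are logged for the pilot patients too.

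**The concern.** The question is one of similarity, and the method tests for difference. A small p-value is evidence that the groups differ. A large one means either that they are alike or that the sample is too small to tell, and with 5 survivors the second explanation is hard to exclude. Sections 3 and 4 ask for a finding either way and tie the reporting of disparities to one of the two answers. Section 9 supplies nothing that could support the other answer.

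At stake is the use that section 2 gives to Aim 2, which is to show where recruitment has gaps. Section 4 expects most admissions not to recover enough neurological function to take part, so real differences between the pilot and all admissions are likely. If a non-significant test were taken as reassurance, those differences could go unreported.

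**Working it through.** The plan states no power or detectable difference for this comparison, so there is no figure of its own to reproduce.

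**Inputs from the documents.** Pilot n = 5 survivors (section 2). Log N = 100 to 400, the outer limits of the two stated ranges (sections 2 and 3). Taking the pilot patients out leaves 95 to 395 comparators. The continuous variables are age and time to ROSC. The categorical ones are location, rhythm and sex (section 6).

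**Assumptions.** Two-sided alpha 0.05, normal data, shifts of 0.5, 1.0 and 1.4 SD, and the category rates used below. None of these is in the documents.

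**Continuous variables, approximate formula.** In SD units, SE = √(1/5 + 1/N).
- N = 95: SE = √(0.2000 + 0.0105) = 0.459. For a 0.5-SD shift, 0.5/0.459 = 1.09. Power ≈ Φ(1.09 − 1.96) + Φ(−1.09 − 1.96) ≈ 0.19, so the miss rate is about 81%.
- N = 395: SE = √(0.2000 + 0.0025) = 0.450. Power ≈ 0.20, so the miss rate is about 80%.

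The 1/5 term dominates, so the conflict between the two log sizes hardly changes the result.

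**Continuous variables, simulated rank-sum test** (20,000 runs per setting, N = 95, 195, 295 and 395):

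| True shift | Missed |
|---|---|
| 0.5 SD | 82-83% |
| 1.0 SD | about 45-47% |
| 1.4 SD | 17-19% |

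If the 5 pilot patients are also left inside the admissions group, the miss rate at 0.5 SD is about 83-86%.

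**Categorical variables, none of 5 against 40%.** With N = 95, the comparator has 38 of 95 and the pooled proportion is 38/100 = 0.38.
- z = 0.40 / √(0.38 × 0.62 × (1/5 + 1/95)) = 0.40/0.223 = 1.80, so Pearson p = 0.072.
- With N = 395 (158 of 395), p = 0.069.
- Fisher's exact p is 0.15 to 0.16.

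Complete absence of a group that makes up 40% of admissions is therefore not flagged at 0.05.

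**Categorical variables, pilot rate 60% against 30%.** With the comparator held at 30%, only 4 or 5 of 5 gives p < 0.05, by Pearson or Fisher. The chance of that is 5 × 0.6⁴ × 0.4 + 0.6⁵ = 0.259 + 0.078 = 0.337. The miss rate is 1 − 0.337 = 66%.

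**What an interval would show.** Exact (Clopper-Pearson) 95% limits are 0-52% for 0 of 5 and 5-85% for 2 of 5. For a mean difference the half-width is 1.96 × SE: 1.96 × 0.459 = 0.90 SD at N = 95 and 1.96 × 0.450 = 0.88 SD at N = 395.

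**The case against.** A reader might infer that the plan has a rule under which a non-significant test means the sample is representative. It does not. No section states such a rule or any significance threshold, and section 9 speaks of context and of examining differences. What stands against the plan is narrower: sections 2 to 4 require a finding, and section 9 offers no criterion that could support a favourable one.

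A reader might also infer that the tests would almost never reject, so that even gross differences would pass unseen. The figures do not support that. A 1-SD shift is detected a little over half the time and a 1.4-SD shift more than 80% of the time. The rates above are also per test, and there are five variables. Suppose time to ROSC differs by 1 SD, one category is 60% against 30% and the other three variables do not differ. If the tests are independent, the chance that nothing is flagged against one comparator is between 0.45 × 0.66 × 0.95³ = 0.25 and 0.47 × 0.66 × 0.95³ = 0.27. Positive correlation would raise it. So large differences would often produce some signal. The weakness is greatest for moderate differences and for differences confined to one variable.

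Three further points limit the reach of the concern:
- Section 4 already tells readers that the pilot is a selected group, which makes a bare claim of representativeness less likely.
- Setting MGH admissions beside US patients, also part of Aim 2, does not rely on the 5 survivors.
- No feasibility or acceptability benchmark, eligibility decision or safety question depends on these tests.

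All three stand. They lower the stakes, but they do not give the tests the ability to establish similarity.

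**Conclusion.** The concern holds as a mismatch between question and method. The only analysis specified for the pilot comparison can support a finding that the pilot differs, but not a finding that it is representative. A non-significant result would leave the question open, and the plan does not say so.

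The size depends on assumed values: two-sided alpha 0.05, normal data, non-overlapping groups and illustrative effects. The 82-83% miss rate applies to a 0.5-SD shift in age or time to ROSC only. For location, rhythm and sex the result depends on the rates, and the 66% miss rate at 60% against 30% is one example. The conclusion does not depend on which log size is right. Changing the plan would be a cheap improvement to how one part of Aim 2 is reported. The concern does not touch the pilot's main results.

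**What to change.** In section 9, make description the primary analysis for the pilot comparison:
- For each logged variable, show the pilot value beside the MGH and US values, with the difference.
- For location, rhythm and sex, give exact 95% intervals for the pilot proportions.
- For age and time to ROSC, list the 5 individual values against the MGH median and quartiles.
- Add a sentence such as: 'Observed differences will be described whatever the p-value; a non-significant test or a wide interval will be reported as inconclusive, not as evidence of representativeness.'

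The tests may stay as secondary. Sections 3 and 4 should be reworded, or at least read, as describing how the enrolled sample differs from admissions.

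The cost is a few sentences, with no new data or patients. The downside is that intervals from 5 survivors are wide, most comparisons will be reported as inconclusive, and the pilot cannot be called representative. Five survivors could not have supported that claim under the present wording either.
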